8.2.3 Electrocardiogram assessment

During ECG study following parameters would be registered: HR and PQ, QRS and QTc (Frederichi method based correction) as well as deviations of ECG outlines from normal values (see Section 4.5.5.5).

8.2.4 US-examination

US-examination of kidneys, bladder and urine excretory ways includes residual urine volume assessment.

8.3 Adverse events and intercurrent diseases reporting

8.3.1 Serious adverse event definition

Adverse event is considered to be any untoward medical occurrence in a patient or clinical study

subject administered a medicinal product and which does not necessarily have a causal relationship with this treatment. Therefore AE can be attributed to adverse and unintentional signs (including deviations of laboratory parameters), symptoms and diseases, demonstrating temporal relationship with application of medicinal (test) product, independently from causal relationship with medicinal (test) product.

Following issues are considered to be AE:

- Laboratory parameters, exceeded the threshold of normal values and clinically significant.
- Laboratory parameters, changed against baseline parameters of the patient and clinically significant.
- Preexisting findings on physical examination, deteriorated in comparison to baseline parameters, and considered to be clinically significant.
- Physical examination findings (including vital parameters) which are considered to be clinically significant.

8.3.2 Adverse events reporting

Investigator-physician and medical center employees bear responsibility for detection, provision of essential medical care, documentation and reporting concerning cases, corresponding to AE and Serious adverse events (SAE) definitions.

Any AE not considered to be serious, will be reported from the moment of start of administration of the study products and before the end of follow-up period (30-35 days after the last receipt of the products). SAE will be registered up to the moment of informed consent signing and will be followed up to their resolution or stabilization of patient condition.

Investigators should document in patients' records and CRF any AE, appeared in patient during the study period. Patient is warned that he/she has to inform his attending physician about any new symptoms evolving.

AE are registered base on complaints, provided by patient personally, results of conversations between investigator and patient, physical examination results and laboratory assessments. Investigator should phrase the questions to the patients not to instigate to presentation of false information.

AE are recorded in the correspondent sections of CRF as well as primary medical documents of the patient.

Following information should be provided during registration of the AE:

- Patient identification code;
- AE classification according to CTC AE V4 classification (if applicable).
- AE features (diagnosis is preferable, not the symptoms list);
- Date of development and resolution of AE (and time, if applicable);
- AE severity;
- Actions taken in respect to the AE;
- Actions, taken in respect to the study product;
- Correspondence of AE to serious adverse event criteria;
- Presence on interrelation between AE and application of the study product (according to Investigator's assessment);

- Outcome of the AE.

Additional procedure is required for SAE (see Section 8.3.5).

8.3.3 Determination of adverse events parameters

In accordance with the current guidances, AE parameters concerning seriousness, foreseeability, severity grade, outcome and causal relationship will be assessed the following way:

Seriousness:

An adverse event is considered to be any adverse medical event, which:

- Resulted in death;
- Was life-threatening;
- Resulted in persistent or significant disability or incapacity;
- Required in-patient hospitalization or prolongation of existing hospitalization;
- Was a congenital anomaly/birth defect;
- Was medically significant event (required measures for prevention of the above mentioned outcomes).

Foreseeability:

“Unintentional” adverse event/reaction does not comply by its nature and severity grade those AE, which are listed in the current version of Investigator’s Brochure or instructions for medical use of the product.

Severity grade:

AE severity is assessed according to the following criteria:

- Mild: Non-interfering with daily activity
- Moderate: Interferes with daily activity
- Severe: Patient is unable to manage with daily activity

Serious AR may not be serious and, conversely, serious AE is not obligatory serious.

In case of AE “dry mouth” severity of this event will be interpreted the following way:

- Mild: Dry mouth presents but scarcely bothers.
- Moderate: Dry mouth is tolerable after water/other liquid intake.
- Severe: Dry mouth is intolerable even after water/other liquid intake; requires therapy withdrawal

Outcome:

AE outcome is assessed following way:

Death	Patient died due to AE (death is considered to be outcome, not AE)
Deterioration	AE deterioration
Unchanged	AE not resolved
Resolved with consequences	AE resolved, but several residual effects continue to persist
Resolved without consequences	AE entirely resolved without any residual effects
Not known	AE outcome is not known because patient did not appear for

	visit of the follow-up examination and attempts to obtain information are fruitless (inaccessibility for further observation).
--	--

Causal relationship:

Causal relationship between each AE, according to WHO criteria, is determined by the following nomenclature:

Unrelated	
 – Presence of a clear alternative explanation and/or – Unreasonable temporal relationship between the drug administration and AE and/or – Implausibility
Inaccessible/ Unclassifiable	– report contains proposal concerning adverse reaction, however it is impossible to consider relationship because information is not sufficient or contradictory, data cannot be completed or validated.
Conditional/Unclassified	
 – events including deviation of laboratory parameter – more data are required for appropriate assessment – additional data are pending issue at the present time
Unlikely related	event including deviation of laboratory parameter with inconclusive (implausible) temporal connection with administration of the product, which, however, does not exclude possibility of this connection other factors, e.g. primary and concomitant diseases, or other medicinal products, could be more probable reasons for AE
Possible	
event including deviation of laboratory parameter possess strong temporal connection with administration of the product
 
AE may also be associated with concomitant diseases or any other medicinal products of chemical substances.
 
Information concerning product withdrawal is not available or requires and upgrade.

Probable/Likely	
 – event including deviation of laboratory parameter possess strong temporal connection with administration of the product – AE is unlikely associated with concomitant diseases or any other medicinal products of chemical substances. – clinically significant response on product dechallenge – repetitive prescription of the product was not performed
Certain	
event including deviation of laboratory parameter possess strong temporal connection with administration of the product
 
AE is not explainable by concomitant diseases or application of other medicinal products or chemical substances.
 
causal relationship with administration of the study product and its withdrawal is justified from biological point of view
 
AE is considered to be identified risk for application of the product
 
AE appears again following repetitive administration of the product (if applicable)

Actions, that should be taken in case of AE appearance:

- change of study product dose
- revocation or suspension of the study product
- prescription of additional medicines (which, what dose, how long) for AE treatment;
- no actions taken

8.3.4 AE follow up observation period

All AE should be followed up to their resolution or up to the moment when physician considers them as “chronic” or “stable”.

In case of serious AE patient observation is performed up to its resolution, using telephone calls with requirement for complains and history taking, as well as during unplanned visits required from patient’s safety point of view.

In case when, according to Investigator physician opinion, AE, not considered to be serious, requires further observation of the patient, this observation may be also performed by telephone calls and visits with inquiry of complaints and patient’s history.

In case of SAE appearance, according to investigator physician assessment, with possible connection with administered product, observation and required treatment is performed dependent on SAE development terms; patient observation is also performed before resolution of SAE.

All additional information concerning AR should be recorded in the correspondent pages of eCRF in the form of additional reports.

8.3.5 SAE report

8.3.5.1 Investigator’s responsibility

AE seriousness assessment is performed by Investigator or his/her authorized representative.

Investigator should inform about any SAE independently from assessment of causal relationship with the study product to the Sponsor’s authorized pharmacovigilance representative (contact information see below) by fax or by e-mail within 24 hours after their development or receiving information concerning SAE.

Primary contact person for SAE cases reporting is Sponsor of the study (R-Pharm JSC).

Authorized pharmacovigilance representative of the Sponsor company will obtain from investigator completed SAE forms, verify their comprehensiveness and specify missing data (whether required). Sponsor may delegate several procedures to CRO including checking CRF and refinement of missing data from investigators. Interaction between CRO and the Sponsor, submission of SAE cases to the Regulatory authorities will be performed in accordance with Standard operational procedures of the Sponsor.

Contact information for safety issues reporting: Sponsor:

Head of Medicinal Products Safety Department of R-Pharm JSC [REDACTED]

[contact] ext. [REDACTED] [contact]

e-mail: [contact]; [REDACTED]

Contract research organization:

Authorized person on pharmaceutical safety

Synergy Research Group OOO

[contact] [contact]

e-mail: [contact]

In case of additional questions Investigators should get in contact with monitor of the corresponding center or Medicinal Products Safety Department of R-Pharm JSC.

SAE report should be prepared independently from assessment of causal relationship with the study product.

If SAE, associated with application of study product, is registered in patient, correspondent report should be submitted even in case when the study has been finished.

Observation over SAE and AE of special interest, as well as AE, causing withdrawal from the study, is performed up to their resolution or stabilization of patient's condition.

8.3.5.2 Notification of regulatory authorities about serious adverse reactions cases

Reporting about suspected unexpected serious adverse reactions (SUSAR)

Authorized pharmacovigilance representative of the Sponsor company will submit information concerning SUSAR towards regulatory authorities of the countries, participating in the study.

Authorized pharmacovigilance representative of the Sponsor company will also inform investigators concerning any SUSAR, reported during the study course.

Investigator will send all information, obtained from Sponsor, about SUSAR, into Local Ethics Board (LEB) of the research center and will store all information, associated with safety report, into Investigator's file.

SUSAR reports, caused death or life-threatening for the patient, should be submitted to regulatory authorities within 7 consecutive days after receipt of information by authorized pharmacovigilance representative of the Sponsor company, and further reports with additional information – within 8 consecutive days. Similar terms for non-life threatening SUSAR are considered to be 15 consecutive days.

Other safety reports application

Authorized pharmacovigilance representative of the Sponsor company will submit to the regulatory authorities reports concerning other safety aspects entitled to immediate notification of these authorities in case they are having an impact on assessment of benefit-risk ratio, connected with treatment applied or may require application of significant corrections into treatment performed under the study conditions, or into study methodology.

Besides immediate reporting, Sponsor company will be preparing annual safety reports for the study product, including all new information, obtained within report period. during the whole study period. These reports will be annually submitted be Sponsor to the regulatory authorities or in different terms on remand of these authorities.

8.3.6 Pregnancy

Pregnancy itself is not considered to be AE, excluding the cases where it is reasonable to presume that application of the study product brought to decreased efficiency of birth control measures. Congenital anomalies/birth defects in patients' children are considered to be SAE. Scheduled abortions, performed for medical indications, with complications, as well as any serious complications during pregnancy (including miscarriages), should be recorded as SAE. Non-complicated scheduled artificial abortions are not considered as AE.

All pregnancy cases occurred within the study period (including pregnancy cases of sexual partners of male patients, participating in the study), should be recorded in an appropriate manner. In case of confirmed pregnancy Investigator should inform authorized pharmacovigilance representative of the Sponsor company through special report form for pregnancy occurrence. Then Investigator should render information to the Sponsor company concerning pregnancy outcome. Female patients and patients' female partners pregnancy cases are recorded from the start of administration of the study product and up to the last study procedure.

Outcomes of all pregnancy cases (spontaneous abortion, elective artificial abortion, healthy child birth or birth of child with congenital anomaly/birth defect) should be recorded.

9 STATISTICS

Statistical analysis will be performed by CRO. Any deviations from assessment order should be included into the Plan to be submitted within the Clinical study report.

Interim analysis during the study is not scheduled. Statistical analysis will be performed using software packet SAS[®] 9.3 or other commercially available software.

9.1 Statistical methods

All values of analyzed parameters will be provided in Tables and graphically represented.

9.1.1 Data description

All registered characteristics of the patients, including demographic data, will be provided in tables as frequency-based and/or percent-based parameters, or using mean, standard deviation, median, minimum and maximum, upper and lower quartiles dependent on variable type. Data will be provided for all patients from the studied population according to the treatment groups. Validation of variables distribution for normality using Kolmogorov-Smirnov test will be performed for assessment of possibility for application of parametric methods.

9.2 Patient population justification

H_0 (null hypothesis): effect of Urotol (tolterodine) according to assessment of mean daily urination episodes exceeds effect of Uritos[®] (Imidafenacin) with non inferiority threshold 0.8 episodes per day.

H_1 (alternative hypothesis): effect of Uritos[®] (Imidafenacin) according to assessment of mean daily urination episodes exceeds effect of Urotol (tolterodine) with non inferiority threshold 0.8 episodes per day.

$H_0: \mu_A - \mu_B \geq \delta$ $H_1: \mu_A - \mu_B < \delta$,

where μ_A, μ_B – efficiency of medicinal products Uritos[®] (Imidafenacin) and Urotol (tolterodine), respectively; δ – non-inferiority threshold ($\delta = 0,8$ episodes per day)

Following levels of error of the first kind = 0.025 and error of the second kind = 0.2 were taken for calculation of the study sample (that corresponds to 80% power of the study), acceptable non-inferiority threshold at the primary endpoint at Week 12 - 0.8 episodes per day; based on results of previous examination of imidafenacin, standard deviation at the primary endpoint is considered to be 2.12 episodes per day on sample consisting from 355 patients.

Sample size calculation is based on formula from [36]:

$$n_A = \frac{(r+1)\sigma^2(Z_{1-\beta} + Z_{1-\alpha})^2}{r((\mu_A - \mu_B) - \delta)^2}$$

Where $r = n_A/n_B$,

σ – assumed standard deviation for change in mean daily number of urination episodes.

n_A, n_B – study group and control group sizes, respectively.

μ_A, μ_B – assumed mean change of mean daily urination episodes in study group and control group, respectively.

$Z_{1-\alpha}, Z_{1-\beta}$ – cumulative function parameters of normal standard distribution for first (α) and second (β) types of errors, respectively.

δ – non-inferiority threshold.

With due consideration of homogeneous distribution of patients among treatment groups ($n_A = n_B$ if $r = 1$), in each treatment group will be randomized

$$n = \frac{2 \cdot 2.12^2 (0.84 + 1.96)^2}{0.02} = 111$$

Sample containing 222 patients (111 per study group) is considered to be sufficient for proof of alternative hypothesis (rejection of null-hypothesis) at the significance level 0.025% and study strength 80%. With due consideration of withdrawal during treatment total amount of patients to be randomized is about 300 (150 patients per study group).

9.3 Significance level applied

All analysis types used in the study will be performed at the statistical significance level < 0.05 if otherwise noted.

During assessment of significance of discrepancies in primary endpoint access one-sided 97.5% confidence interval will be applied.

Two-sided 95% confidence intervals will be applied during description and testing of other data.

9.4 Interim analysis and study cessation criteria.

Not applicable

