	
Sample containing 222 patients (111 per study group) is considered to be sufficient for proof of alternative hypothesis (rejection of null-hypothesis) at the significance level 97.5% and study strength 80%. With due consideration of withdrawal during treatment total amount of patients to be randomized is about 300 (150 patients per study group).
 
For treatment efficiency assessment (primary endpoint) one-side 97.5% confidence interval for arithmetic mean values of primary endpoint will be calculated. In other cases of comparison two-sided 95% confidence intervals will be utilized.
 
Changes will be considered as significant at $p < 0.05$.
 
For comparison of AE appearance in the study groups χ^2 test of exact Fisher test is planned to be applied, for comparison of manifestation rate Mann-Whitney U test will be applied.
 
Laboratory parameters (total blood count and blood biochemistry, urinalysis), vital parameters will be assessed separately to each group with the following comparison using paired Student t-test for connected samples (for parameters with normal distribution) or using non-parametric Wilcoxon signed rank test for connected samples (for parameters with ordinary scale type or in case of significant distribution deviations from normal).

--	--

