3 OBJECTIVES AND TASKS OF THE STUDY

Study objective:

Assessment of clinical efficiency and safety of the medicinal product Uritos® (Imidafenacin) in comparison to the medicinal product Urotol (tolterodine) for the indication of overactive bladder (OAB) treatment.

Study objectives:

- Determination of clinical efficiency of the product Uritos® (Imidafenacin) in comparison with the product Urotol (tolterodine) according to its influence on urination frequency and number of urinary incontinence episodes. Safety assessment of the medicinal product

Uritos® (Imidafenacin) in comparison to the medicinal product Urotol (tolterodine).

- Perform safety assessment of the medicinal product Uritos® (Imidafenacin) in comparison to the medicinal product Urotol (tolterodine).

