4 STUDY DESIGN

4.1 Study endpoints/efficiency criteria

Primary efficiency criteria:

Change of mean daily number of urination episodes at the 12 week Visit against the Visit of starting therapy.

Secondary efficiency criteria:

1. Change of mean daily number of urinary incontinence episodes at the 12 week Visit against the Visit of starting therapy.
2. Change of mean daily number of urinary incontinence episodes during daytime (from 7 am to 11 pm) at the 12 week Visit against the Visit of starting therapy.
3. Change of mean daily number of urinary incontinence episodes during nighttime (from 11 pm to 7 am) at the 12 week Visit against the Visit of starting therapy.
4. Change of mean daily, mean daytime and mean nighttime number of urinary incontinence episodes at the weeks 2, 4, 8 Visits against the Visit of starting therapy.
5. Change of mean number of urinary incontinence episodes per week at the 12 week Visit against the Visit of starting therapy.
6. Change of mean daily number of urinary incontinence episodes at the weeks 2, 4, 8 Visits against the Visit of starting therapy.
7. Changes in overactive bladder symptoms assessment parameters according to Overactive bladder Awareness Tool Questionnaire at Visits 2, 4, 8 and 12 weeks in comparison to the visit before the beginning of therapy.
8. Change of quality of life assessment using EQ-5D questionnaire (at the 12 week Visit against the Visit of starting therapy).

4.2 Justification and brief description of the study design.

[figure not shown]
International multicentral (performed in several research centers within the territory of Russian Federation and Belarus Republic), open-label, randomized comparative (parallel-group) efficiency and safety clinical study, where patients group, taking medicinal product Uritos[®] (Imidafenacin), is considered to be test group, and group, taking medicinal product Urotol (tolterodine) is considered to be active control group (comparator product group). Non-inferiority assessment study.

No more than 350 patients are planned to be screened and 300 patients are planned to be randomized (150 per study group), that, with due consideration of assumed withdrawal during treatment period, will give at least 222 patients completely finished the study (111 patients per study group).

Parallel study design was selected in scientific purposes.

Study design is presented on the Figure 1. and detailed description is presented in the Section 4.5.3.

Fig. 1 Study scheme

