9.8 Efficiency assessment

Efficiency assessment of mean daily, mean daytime and mean nighttime number of urinary incontinence episodes / urination at the Week 2, 4, 8 and 12 Visits, including analysis based on primary efficiency criteria, as well as mean number of urinary incontinence episodes per week at the Week 12 – will be performed with the use of covariance analysis (ANCOVA). Number of urinary incontinence episodes / urination at the Visit of start of therapy will be used as covariate, and therapy group will be used as factor. Primary efficiency analysis according to primary efficiency criteria will be performed in FAS and PP populations. For evaluation of hypothesis of “non-inferior” efficiency upper border of one-side 95% confidence interval for difference in evaluation of mean daily number of urinations among test product and control product tolterone will be calculated. During comparison of therapy groups according to other efficiency criteria two-sided 95% confidence intervals will be built. Comparison of therapy groups on efficiency criteria: change in Overactive Bladder Awareness Tool Questionnaire (OAB Awareness Tool) and change in Quality of life by Quality of life Questionnaire EQ-5D will be performed following data validation concerning their normality, distribution using Kolmogorov-Smirnov criteria. In case of normal distribution data will be compared using Student’s t-test, otherwise non-parametric Mann-Whitney criteria will be used.

Primary efficiency analysis according to secondary efficiency criteria will be performed in FAS and PP populations.

Kolmogorov-Smirnov test for normal distribution and heterogeneous dispersion test using Leven criteria will be also performed during every visit as additional assessments in FAS population for mean daily, mean daytime and mean nighttime number of urinations and urinary incontinence episodes at Weeks 2, 4, 8 and 12. In case when one of these tests is apparently statistically significant ($p < 0.05$), comparison between therapy groups will be performed using non-parametric Mann-Whitney criteria.

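### Every secondary efficiency comparison is tested at two-sided 0.05 and may be called significant, with no order, gate on the primary result, multiplicity control or supportive label

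*Combined protocol and SAP*

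**What the plan says.** Section 9.3 of the combined protocol and SAP states: "All analysis types used in the study will be performed at the statistical significance level < 0.05 if otherwise noted" (the sense is presumably *unless* otherwise noted). The exception is the primary endpoint, which has its own one-sided interval. For everything else, 9.3 says: "Two-sided 95% confidence intervals will be applied during description and testing of other data". Section 9.8 repeats this for efficacy: "During comparison of therapy groups according to other efficiency criteria two-sided 95% confidence intervals will be built". The synopsis (1.3) adds a general rule that opens "Changes will be considered as significant at" and gives p < 0.05 as the cut-off.

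The secondary criteria are items 1 to 8 of section 4.1, repeated in 7.1 and the synopsis. Item 4, for example, reads "Change of mean daily, mean daytime and mean nighttime number of urinary incontinence episodes at the weeks 2, 4, 8 Visits". Section 9.8 then extends the covariance analysis to daily, daytime and nighttime urination at all four visits, and adds: "Primary efficiency analysis according to secondary efficiency criteria will be performed in FAS and PP populations".

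No section gives an order of testing, a condition on the primary result, a split of alpha, a multiplicity adjustment, or an exploratory or descriptive label for the secondary criteria.

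**The concern.** The plan names one primary contrast and gives it its own error rate, but leaves the secondary family open. Each member is tested at the full two-sided 5%, and the plan's own language is of testing and significance, not only of description. With this many comparisons, two drugs of equal effect have a substantial chance of producing a nominally significant difference somewhere.

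Two features make this matter here. Section 2 says the trial is meant to support registration, and section 3 states the efficacy objective as comparing the drugs "according to its influence on urination frequency and number of urinary incontinence episodes". Incontinence therefore sits beside urination frequency in the objective, although it is only a secondary criterion and is divided into 12 comparisons. A chance result on one of them, such as nighttime incontinence at Week 4, could be presented as answering the objective. Nothing in the plan says how such a result should be read, or ties it to the primary outcome. The study is also open-label with diary-based outcomes, so isolated differences already need caution.

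**Working it through.** **Counting the contrasts** (sections 4.1, 7.2 and 9.8; duplicates counted once)

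- Incontinence at Week 12, items 1 to 3: 3 (daily, daytime, nighttime).
- Incontinence at Weeks 2, 4 and 8, item 4: 3 measures × 3 visits = 9.
- Item 5 (per week, Week 12): 0 extra. Section 7.2 computes it with the same numerator and divisor as the daily mean.
- Item 6 (daily, Weeks 2, 4 and 8): 0 extra, since item 4 already contains it.
- OAB Awareness Tool, item 7: 4 visits = 4.
- EQ-5D, item 8: 1 (2 if the index and the visual analogue scale are both compared).

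Listed total: 3 + 9 + 4 + 1 = 17. Counting the list literally, with items 5 and 6, gives 17 + 1 + 3 = 21.

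Section 9.8 adds urination: 3 measures × 4 visits − 1 (the primary) = 11. That makes 17 + 11 = 28.

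**Chance of at least one false difference**

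The plan states no error rate for the secondary family, so there is no figure of its own to reproduce. It also gives no correlation between endpoints or visits, so the correlation below is an assumption and is shown over a range.

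For k independent tests at two-sided 0.05 the chance is 1 − 0.95^k:

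- k = 17: 1 − 0.95^17 = 58.2%
- k = 28: 1 − 0.95^28 = 76.2%

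For normal test statistics with common correlation ρ and c = 1.96 it is

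1 − ∫ [Φ((c − √ρ·u)/√(1−ρ)) − Φ((−c − √ρ·u)/√(1−ρ))]^k φ(u) du.

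For false results in one direction only, the bracket becomes Φ((c − √ρ·u)/√(1−ρ)). At ρ = 0 this reduces to 1 − 0.975^k.

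| ρ (assumed) | 17, either direction | 17, favouring imidafenacin | 28, either direction | 28, favouring imidafenacin |
|---|---|---|---|---|
| 0 | 58.2% | 35.0% | 76.2% | 50.8% |
| 0.3 | 49.3% | 25.4% | 64.1% | 33.8% |
| 0.5 | 38.6% | 19.4% | 49.1% | 24.7% |
| 0.7 | 27.1% | 13.5% | 33.0% | 16.5% |
| 0.9 | 14.9% | 7.4% | 16.9% | 8.5% |

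**Check with a more realistic structure.** A simulation of 200,000 trials per setting made the daily score the sum of daytime and nighttime. It used correlations over time of 0.3 to 0.9, between day and night of 0.3 to 0.7, and between domains of 0.1 to 0.5. The chance in either direction was about 24% to 48% for 17 contrasts and 32% to 65% for 28, which lies inside the ranges in the table.

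**Week 12 alone.** The five distinct Week 12 secondaries (three incontinence measures, OAB Awareness Tool, EQ-5D) give 22.6% at ρ = 0, 18.3% at 0.5 and 10.2% at 0.9, in either direction.

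**Primary test.** Section 9.2 sizes it at one-sided 0.025 and 80% power: 2 × 2.12² × (0.84 + 1.96)² / 0.8² = 110.1, so 111 per group. None of these inputs depends on the secondary tests.

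**The case against.** The strongest reply is that the trial's conclusion is already protected. There is one primary criterion at one time point, with its own hypotheses and one-sided error of 0.025, and no interim look. All three endpoint lists place incontinence under the secondary criteria, which ranks it below the primary. No section plans a superiority claim from a secondary result. The 0.05 in 9.3 is a level for each analysis; the plan promises no 5% rate across the family, so no stated error rate is breached. All of this stands, and it limits the point to how secondary results may be described.

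It does not remove the point. The plan does not merely stay silent: it says these data will be tested and that results below 0.05 count as significant. Heading a list as secondary says nothing about how its p-values should be read.

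A reader might infer more than the documents support:

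- *That a false difference is 39% to 49% likely.* Those figures are the 17- and 28-contrast results at one assumed correlation of 0.5. The spread between them reflects only the change in count, not uncertainty.
- *That there are 28 secondary comparisons.* Eleven of them are in no endpoint list and come only from the wording of 9.8.
- *That the per-protocol repeats are further chances to win.* Section 9.7 gives the per-protocol analysis the role of confirming the full-analysis-set conclusions.
- *That these are rates of false claims for imidafenacin.* The either-direction rates include differences favouring tolterodine; the rate in imidafenacin's favour is about half at correlations of 0.5 and above.
- *That the non-inferiority conclusion is inflated.* It is not.

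**Conclusion.** The concern holds as a defect in the stated decision rule for the secondary efficiency criteria. With equal drugs, full two-sided 0.05 tests and an assumed common correlation from 0.9 to 0, the chance of at least one false difference is about 15% to 58% for the 17 listed contrasts and 17% to 76% if the 11 urination contrasts are added. In imidafenacin's favour only, it is about 7% to 35% for the 17. The exact value cannot be known from the documents, but at every correlation tried the either-direction rate for the 17 is well above the 5% that a reader would attach to a single result called significant. The effect is confined to difference claims drawn from secondary results; the primary analysis and the sample size stand. The change is worth making because it is cheap and alters what the trial may claim.

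**What to change.** In 9.3 and 9.8, and matched in the synopsis, add wording to this effect: *Secondary efficiency comparisons are supportive. They will be reported as estimates with two-sided 95% confidence intervals and nominal p-values, unadjusted for multiplicity. No confirmatory claim, and no statement of a significant difference, will be based on them.* Limit the p < 0.05 rules in 9.3 and the synopsis so that they no longer cover these comparisons. The same sentence should cover the urination contrasts that appear only in 9.8.

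If the sponsor wants a confirmatory secondary claim, it should choose and pre-specify its own short fixed sequence in the full analysis set, entered only once primary non-inferiority has been shown, with everything outside the sequence remaining supportive. This is optional.

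The cost is a few sentences in an amendment. No data, patients or analyses are added, and 111 per group is unchanged. The sponsor gives up the ability to call an isolated secondary p < 0.05 a significant difference.
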